Specific Aim 2: In a waitlist-controlled trial, we will test the efficacy of the active treatment arm compared to a waitlist in reducing secondary outcomes (e.g., delusionality, quality of life, social and occupational functioning, depression) at end-of-treatment (week 12).

Secondary Hypothesis: We hypothesize that participants receiving app-based CBT for BDD will have greater improvement on secondary clinical outcome measures (i.e., depression (QIDS-SR), delusionality (BABS), functional impairment (SDS), and quality of life (Q-LES-Q)) than those in the waitlist condition at treatment endpoint (week 12).

III. SUBJECT SELECTION

Overview:

Massachusetts General Hospital was responsible for all participant recruitment and enrollment. We collaborated with Koa Health B.V., a in the testing of the app.

For this Phase 2 randomized waitlist control trial, our target sample size was 80 eligible individuals with primary BDD (for details, see section VI-D “Power analysis”). Detailed eligibility criteria for each aim follow. Additionally, a detailed plan for safety and risk management is described below.

Inclusion/Exclusion Criteria:

1. Inclusion criteria
 - a. at least 18 years of age
 - b. current diagnosis of primary DSM-5 BDD, based on MINI

- c. currently living in the United States

2. Exclusion criteria
 - a. Psychotropic medication changes within 2 months prior to enrollment
 - i. Participants taking psychotropic medication must have been on a stable dose for at least 2 months prior to enrollment and not change medication during study period
 - b. Past participation in ≥ 4 sessions of CBT for BDD
 - c. Current severe substance use disorder
 - d. Lifetime bipolar disorder or psychosis
 - e. Acute, active suicidal ideation as indicated by clinical judgment and/or a score ≥ 2 on the suicidal ideation subscale of the C-SSRS.
 - f. Current severe comorbid major depression, as indicated by clinical judgment and/or a QIDS-SR total score ≥ 21
 - g. Concurrent psychological treatment
 - h. Does not own a supported mobile Smartphone with a data plan
 - i. Lack of technology literacy that would interfere with ability to engage with smartphone treatment

A. Source of Subjects and Recruitment Methods:

Overview:

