Eligible subjects were randomized to immediate app-based CBT for BDD or to a waitlist control condition (50/50 chance). Randomization was stratified by participants' medication status, in order to evenly distribute any potential medication effects on treatment response across both study arms. The waitlist control group allowed us to determine whether active treatment is superior to gains afforded by the passage of time or other extraneous variables (e.g., history, maturation, testing). Those beginning the CBT treatment immediately were taught to download the app and received a brief tutorial in using the app-based treatment. Following the waitlist period, participants randomized to this condition were crossed over to app-based CBT to allow assessment of within-subject treatment gains for control participants. The duration of CBT for waitlist participants was the same as for participants who were treated first with CBT.

Wait Period: To maximize the validity of our study, we matched the duration of the waitlist condition to that of the CBT condition. We successfully used a similar design in the PI's prior BDD trial assessing in-person individual CBT. Furthermore, Veale et al (1996) has shown that patients do not improve on a 12-week waitlist and that this duration is tolerated by BDD patients. To protect the safety of participants assigned to the waitlist condition, participants who had active suicidal ideation at the screening assessment were not eligible to participate in this trial (see Exclusion criteria). Additionally, individuals with severe comorbid major depression were not eligible to participate this trial (see Exclusion criteria). The waiting period for standard care for BDD at MGH is at least 3-6 months. Thus, being on a 3-month waitlist in the proposed study may enable the subject to start treatment sooner than being on the general clinic waitlist. However, we offered referral resources to study candidates who did not wish to be randomly assigned to a possible waitlist condition.

V. STUDY PROCEDURES

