Baseline differences between the treatment arms in demographic and other potential prognostic variables were examined using chi-square analyses for discrete variables (if prevalence >10% in the treatment arm with the lower prevalence, or Fisher's exact test if not) and t-tests for continuous variables. Prior to data analysis, all major variables were screened for inconsistent or abnormal values. Continuous measures were assessed for skewness and outliers (based on model residuals); no data transformations were necessary to meet modeling assumptions of normality and homogeneity of variance. A two-tailed p-value <.05 was considered evidence of statistical significance for the primary and secondary outcomes. Our primary and secondary analyses used generalized linear mixed-effects models (GLMMs). GLMMs can easily accommodate nesting of repeated observations within subjects, include all who complete at least one assessment (including the baseline assessment), and are the preferred method to analyze longitudinal data (Hamer and Simpson, 2009). Despite our best efforts to retain participants, we expected dropouts (subjects who are lost to follow-up or withdraw early from the study). We attempted to perform all scheduled assessments for subjects who were withdrawn from the protocol and provided financial incentives for participation in assessments. Our intent-to-treat sample included all randomized patients who completed at least one assessment, making our primary and secondary analyses intent-to-treat analyses. We also performed "per protocol" analyses. Our per protocol population included all randomized patients who completed the baseline and post-treatment assessments, and who did not initiate prohibited treatment during the study. We repeated our GLMM analyses using the per protocol sample. Dropout, study withdrawal, and loss to follow-up was tabulated by reason and treatment arm. Analyses were conducted to ascertain to what extent dropouts were nonrandom, and, if so, what factors were associated with dropout. To evaluate potential attrition bias, study dropouts were compared to study completers.

A. Specific data variables collected for the study (e.g., data collection sheets)

Specific variables that were collected and their timeline are presented above in Table 1 and described in the Study Procedures section.

B. Study endpoints

Primary endpoint: Difference in BDD severity (BDD-YBOCS) at the end of treatment/waitlist period.

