Hypothesis 1: Participants receiving app-CBT will have greater improvement in BDD-YBOCS scores than those in the waitlist condition at treatment endpoint (week 12).

Secondary endpoints: Difference in secondary clinical outcomes at the end of treatment/waitlist period

Hypothesis 2: Participants who receive app-CBT will have greater improvement on secondary clinical outcome measures (i.e., depression (QIDS-SR), delusionality (BABS), functional impairment (SDS), and quality of life (Q-LES-Q)) than those in the waitlist condition at treatment endpoint (week 12).

C. Statistical methods

Primary endpoint: Preliminary efficacy for reducing BDD symptom severity

Analysis:

The primary outcome model was a hierarchical mixed model (i.e., GLMM) that included time (categorical; baseline, mid-point, and end-of-treatment), treatment (app-CBT vs. waitlist), and their interaction as fixed effects, and modeled time as a repeated measure using either an autoregressive (AR1), Toeplitz, compound symmetry, or unstructured covariance matrix, based on best fit determined by AIC and BIC. The main hypothesis test was based on a specific contrast of treatment difference at week 12. Because these analyses included all subjects who were randomized and completed at least one assessment, it was an intent-to-treat analysis. These analyses included only the 3 assessments from baseline to post-treatment and did not include the follow-up (FU) assessments, because treatment response could be affected by subjects seeking other treatments during the FU period. Between-group effect sizes were calculated using Cohen's *d*. This analysis was then repeated using the per-protocol sample.

In addition to the analyses specified above, we described the proportion of subjects in each treatment arm who achieved response, where response was defined as a 30% or greater reduction in BDD-YBOCS score from baseline to end of treatment (week 12). This empirically derived cut-off of 30% reflects clinically significant improvement and is widely used in BDD treatment studies (Phillips et al., 1997). While no formal comparison was made between treatments, the reporting of response rates is clinically useful and will facilitate comparison to other studies in the field. We reported response as observed (excluding subjects with missing data at week 12).

Secondary endpoint: Preliminary efficacy for secondary outcomes

Analysis:

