We used the same hierarchical mixed model approach as described for the primary endpoint to examine significant differences in secondary outcome measures (i.e., depression severity, delusionality, functional impairment, and quality of life) at posttreatment for treated participants compared to waitlist control participants. We did not adjust for multiple testing among secondary outcomes based on the recommendation of Cook and Farewell (1996), who argue that multiplicity adjustments are not necessary if separate test results are interpreted marginally and address different aspects of the patient experience and decision-making process rather than alternative assessments of efficacy.

D. Power analysis

Pre-COVID-19, the sample size required to test a significant symptom severity difference between the app-CBT and the waitlist control conditions at the end of treatment was estimated to be $n=64$ ($n=32$ per group). The sample size estimates were based on a single degree of freedom contrast in an ANOVA design, implemented in SAS for Windows version 9.4. The power model used a two-sided alpha=0.05, a power of 0.90, equal allocation of participants into both treatment arms (app-CBT vs. waitlist), and an anticipated effect size of 0.9. We further assumed a drop-out rate of 15% by the end of treatment. This anticipated effect size of the app-CBT is in the range of effect sizes calculated using the published estimate of a waitlist control group BDD-YBOCS mean after 12 weeks (source: Wilhelm et al., 2014), compared to either the combined site mean at week 12 in an in-person CBT treatment study for people with BDD ($d=0.93$; Wilhelm et al., 2019) or the mean at week 12 in an internet-based CBT treatment study for people with BDD ($d=1.02$; Enander et al., 2016). More generally, large effect sizes for CBT vs. waitlist are to be expected, based on meta-analysis by Ost and colleagues (2015) for the closely related disorder OCD, which found that the weighted mean effect size of CBT vs. waitlist control was Hedges $g=1.31$, 95%CI: [1.08, 1.55]. The anticipated drop-rate was based on the weighted mean of drop-out rates (14.4%) reported in three studies that examined the efficacy of CBT treatment in participants with BDD: one compared to waitlist ($n=36$, 19.4% drop-out at week 12; Wilhelm et al., 2014), one compared to SPT,

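### Randomisation was stratified by medication status, but the primary, per-protocol and secondary models omit the stratum; adding it is a nearly free, small gain in precision if medication status is prognostic

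*Combined protocol and SAP*

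**What the plan says.** Section IV.B stratifies randomisation by medication status, "in order to evenly distribute any potential medication effects on treatment response across both study arms". The primary model in Section VI.C "included time (categorical; baseline, mid-point, and end-of-treatment), treatment (app-CBT vs. waitlist), and their interaction as fixed effects". The hypothesis test is the treatment difference at week 12.

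The other analyses inherit this specification. For the per-protocol population, Section VI says "We repeated our GLMM analyses using the per protocol sample". For depression, delusionality, functional impairment and quality of life, Section VI.C says "We used the same hierarchical mixed model approach as described for the primary endpoint".

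No section puts medication status into a model or explains leaving it out. The tests of baseline differences between arms in Section VI do not do so. The exclusion criteria in Section III add a partial safeguard: participants on psychotropic medication "must have been on a stable dose for at least 2 months prior to enrollment and not change medication during study period".

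**The concern.** By stratifying, the sponsor treated medication status as a possible influence on response. An analysis that follows the randomisation would carry the same factor. Three things could follow from leaving it out.

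- **Blocked allocation within strata, prognostic stratum.** The design removes the between-stratum variance from the treatment estimate, but the model leaves it in the residual variance. The reported standard error is too large and the test is conservative.
- **Unrestricted allocation within strata, prognostic stratum.** The standard error is valid, but precision is lost.
- **Dropout that depends jointly on medication status and arm.** The arms observed at week 12 then differ in their medication mix, and the unadjusted contrast can carry a small bias. Section VI treats nonrandom dropout as a possibility to be checked: "Analyses were conducted to ascertain to what extent dropouts were nonrandom, and, if so, what factors were associated with dropout".

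At stake is some precision on one primary and four secondary contrasts, and the reader's ability to see whether the result holds under a model that matches the randomisation.

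**Working it through.** **The plan's own figures (Section VI.D).** Inputs: two-sided alpha 0.05, power 0.90, equal allocation, 15% dropout. A two-sample t test, equivalent to the plan's one-degree-of-freedom ANOVA contrast, gives:

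- d = 0.90: 27 evaluable per arm; 27/0.85 = 31.8, so 32 per arm and 64 in total.
- d = 0.81: 34 evaluable per arm; 34/0.85 = 40 per arm and 80 in total.

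Both totals are reproduced. Power at 34 evaluable per arm and d = 0.81 is 90.8% with no stratum term.

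**Assumed inputs.** The documents do not give the share medicated (p), the week-12 gap between medicated and unmedicated participants (δ, in within-stratum SD), the allocation method within strata, or the correlations between visits. The gaps used are 0.3, 0.5 and 0.8; 0.8 is a large example, not a bound.

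**Closed form, exact balance within strata.** The share of week-12 variance explained by the stratum is VE = p(1−p)δ² / (1 + p(1−p)δ²). The standard error is too large by 1/√(1−VE) − 1 = √(1 + p(1−p)δ²) − 1. True type I error is 2(1 − Φ(1.96/√(1−VE))).

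Example with p = 0.5 and δ = 0.5: p(1−p)δ² = 0.0625 and √1.0625 = 1.031, so the standard error is 3.1% too large. Type I error is 2(1 − Φ(1.96 × 1.031)) = 4.3%.

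**Simulation of the three-visit model.** N = 80, half medicated, unstructured covariance, visit correlations 0.6/0.5/0.65, 15% random dropout, d = 0.81 for power, 20,000 runs per cell. Both models were fitted to the same data; the adjusted one adds stratum-by-time. Monte Carlo standard error is about 0.15 point for type I error and 0.2 point for power.

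| Gap at week 12 (within-stratum SD) | 0.3 | 0.5 | 0.8 |
|---|---|---|---|
| Closed form, half medicated: SE too large by | 1.1% | 3.1% | 7.7% |
| Closed form, half medicated: type I error | 4.7% | 4.3% | 3.5% |
| Closed form, 30% medicated: SE too large by | 0.9% | 2.6% | 6.5% |
| Closed form, 30% medicated: type I error | 4.8% | 4.4% | 3.7% |
| Simulation, blocks of 4: type I error without / with stratum | 4.4 / 4.7% | 4.3 / 4.9% | 3.6 / 4.9% |
| Simulation, blocks of 4: power gained by adding stratum (points) | 0.2 | 0.8 | 1.7 |
| Simulation, unrestricted: type I error without / with stratum | 5.0 / 5.0% | 4.8 / 5.1% | 4.8 / 4.7% |
| Simulation, unrestricted: power gained (points) | about 0 | about 1 | about 2.5 |

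A gap of 1.0 SD with half medicated gives, in closed form, a standard error 12% too large and type I error of 2.8%. In the simulations power was about 91% to 95% throughout.

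**Cross-check at week 12 alone.** With 34 evaluable per arm and the stratum in the model, power is 91.4%, 92.2% and 93.4% when the stratum explains 2%, 5% and 10% of the variance. In the same stratified trial, simulation puts the gain over the unadjusted model at about 0.4, 0.7 and 1.5 points. Explaining 5% with half medicated requires a gap of √(0.05/0.25) = 0.45 total SD.

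**Joint dropout.** Suppose dropout is 25% in medicated and 5% in unmedicated app-CBT participants, reversed on the waitlist. Each arm averages 15%. Among those observed at week 12, the medicated share is 0.75/1.70 = 44.1% in one arm and 0.95/1.70 = 55.9% in the other, a difference of 0.118. Using week 12 alone, the bias is 0.118δ = 0.04/0.06/0.09 SD. The mixed model recovers part of this from earlier visits. Its bias is about 0.01/0.02/0.03 SD if the gap is the same at every visit, and about 0.03/0.05/0.08 SD if it appears only after baseline. With the stratum in the model the bias is about 0. Type I error without the stratum stayed at 3.6% to 4.6%.

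**Not tested.** Section VI.C allows the model to be fitted "using either an autoregressive (AR1), Toeplitz, compound symmetry, or unstructured covariance matrix". Only the unstructured case was simulated; standard errors under the other three can differ.

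**The case against.** The strongest reply is that nothing here misleads. The unadjusted contrast is valid, any error in the test is conservative, and the sample size was set without a covariate, so planned power does not depend on adjustment. The size rests on several quantities the documents do not give, and Section IV.B speaks only of potential medication effects. All of this stands, and it is why the point is minor. It does not explain the omission of a factor that the design itself used.

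Three further objections carry less weight.

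- **Stratification and stable dosing already deal with medication.** Stratification balances the arms at baseline but does not correct the model's standard error. The stable-dose rule limits changes during the trial but does not make medicated and unmedicated participants alike in outcome. Nor does having baseline among the repeated outcomes help here: with complete data, the week-12 contrast in this model is the raw difference in week-12 means.
- **The hypothesis speaks of improvement, which could mean change from baseline.** On that reading, a gap that is constant over time cancels, and omitting the stratum inflates the standard error by 0%. If the gap appears only after baseline, the inflation matches the week-12 figures at the visit correlations assumed above. However, the endpoint in Section VI.B and the test in Section VI.C are both the difference at week 12.
- **The dropout pattern is hypothetical.** Nothing in the documents suggests it, and the plan tries to assess participants who withdraw. The bias is small against a planned d of 0.81, and its size depends on how the gap develops: a full gap from week 6 gave about 0.03/0.04/0.06 SD. It is a secondary reason for adjusting, not the main one.

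**Conclusion.** The concern holds as an optional improvement of low priority. The stratification factor is missing from the primary, per-protocol and secondary models without explanation.

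Under blocked allocation and an assumed gap of 0.3 to 0.8 SD, the standard error of the week-12 contrast is about 1% to 8% too large. Across both allocation methods, the power forgone is about 0 to 2.5 points. There is no type I error inflation. There is also no bias, provided dropout does not depend jointly on medication status and arm. If it does, a bias of a few hundredths of an SD is possible.

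If medication status is not prognostic, the omission costs nothing. The direction and rough size are supported. The decimals are not, because they rest on assumed prevalence, prognostic strength, visit correlations and an unstructured covariance.

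**What to change.** Add medication status as randomised, and its interaction with time, as fixed effects in the primary, per-protocol and secondary mixed models. Keep the week-12 contrast as the test. The time interaction lets the medication gap differ between visits, which is needed for the full gain at week 12 if the gap changes.

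Parts of Section VI read as if the analysis is complete, for example "no data transformations were necessary to meet modeling assumptions of normality and homogeneity of variance". If the models have been fitted, keep the specified model as primary and report the stratum-adjusted model beside it, labelled as a post hoc sensitivity analysis. In either case, state whether allocation was blocked within strata.

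The cost is one covariate already recorded at randomisation and about three degrees of freedom, one per time point. If medication status is not prognostic, simulated power changes by about 0 points under blocking and −0.4 point under unrestricted allocation, so at most about half a point is lost.

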Following screening and randomization, participants completed self-report measures for the baseline assessment through a secure REDCap link emailed to them. In this trial, we aimed to evaluate changes in primary symptoms as well as to examine secondary and exploratory outcomes, including treatment feasibility and acceptability (e.g., retention and reasons for treatment refusal and dropout, expectancy, and motivation), and changes in depression, functional impairment, delusionality, and quality of life. Therapeutic progress will be broadly assessed with measures of beliefs, behaviors, mood, functioning, and quality of life before, during, and after treatment.

Study Visits and Procedures

Phone Screen: Phone screen procedures were as described above.

Screening Calls and Randomization Procedures: Procedures were as described above.

Assessments: Participants in both conditions were assessed at regular intervals: at baseline (week 0), mid-treatment (week 6), end-of-treatment (week 12), and a 3-month follow-up visit (for details, see Table 1 below). Masters or doctoral-level study IEs conducted clinician-rated assessments, and participants completed self-report questionnaires on the computer via REDCap, a secure data capture system. Please see the schedule of assessments and measures administered (relevant to the primary and secondary aims of this trial) at each time point in Table 1. Assessments required approximately 1 hour. These assessment lengths are like those used in other studies in our program and have been well-tolerated by participants. To avoid dropout, participants were paid \$25 for mid-waitlist, end-of-waitlist, mid-treatment, end-of-treatment, 3-month follow up assessments, and 12-month follow-up assessments. Despite our best efforts to retain participants, we expected dropouts. Except for subjects who withdrew consent to participate, all

who were withdrawn or dropped out of the study were asked to complete all scheduled assessments and were provided remuneration for participation in assessments.

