3-month Follow-up Feedback to Technologists: Participants could choose to meet with technologists from Koa Health (sponsor) via a Partners-approved, secure, HIPAA-compliant clinical video platform (Healthcare secure Zoom) at the 3-month follow-up, for the technology experts to obtain input and feedback on the usability and feasibility of the CBT app. This meeting would take approximately 1.5 hours, and participants would be reimbursed \$25 for completion of the 3-month follow-up feedback visit with technologists.

Table 1: Measures table

Measure	RANDOMIZED CONTROL TRIAL: ARM 1								COMPASSIONATE CARE (WAITLIST CONDITION CROSSES TO APP)			
	Baseline	Baseline Re-assess	Weekly	Week 4	Mid-Treatment Assess (wk 6)	Post-Treatment Assess (wk 12) †	3-month Follow-up*	12-month Follow-up*	Weekly	Week 4	Mid-Treatment Assess (wk 6)	Post-Treatment Assess (wk 12)
Treatment History Checklist	✓											
Treatment History Medication	✓											
Treatment History Psychosocial	✓											
AE Form		✓			✓	✓	✓	✓			✓	✓
Body Parts of Concern Checklist (BPCC)	✓											
BDD Y-BOCS	✓	✓			✓	✓	✓	✓			✓	✓
BABS	✓	✓			✓	✓	✓	✓			✓	✓
MINI	✓											
C-SSRS Lifetime	✓											
C-SSRS Update		✓				†						
CGI-C	✓	✓			✓	✓	✓	✓			✓	✓
Treatment Condition Questionnaire						✓						
CONCOM Form		✓			✓	✓	✓	✓			✓	✓
BDD-PSR	✓	✓			✓	✓	✓	✓			✓	✓
Life Events Question		✓			✓	✓	✓	✓			✓	✓
Technologist Interview Notes						✓						
PHQ-2			✓						✓			
QIDS-SR – Q12			✓						✓			

CGI-P		✓	✓		✓	✓	✓	✓	✓	✓	✓	✓
Demographics	✓											
Lifetime Psychiatric Medications	✓											
Credibility Expectancy Rating [~]	✓				✓	†				✓		
QIDS-SR	✓	✓			✓	✓	✓	✓		✓		✓
QLESQ	✓				✓	✓	✓	✓		✓		✓
SDS	✓				✓	✓	✓	✓		✓		✓
CSQ [~]					✓	✓				✓		✓
Treatment Utilization Questionnaire [~]					✓	✓	✓			✓		✓
App Feedback Questionnaire (Endpoint) [~]						✓						✓
App Feedback Questionnaire (Baseline) [~]	✓					†						
App Feedback Questionnaire (Midpoint) [~]					✓					✓		

If more than ten days elapse between a patient's initial baseline screening assessment and the start of treatment, the study IE would re-administer the AE form, AE log, BDD-YBOCS, BABS, CONCOM form, CMED log, and CThERAPY log to that participant, and they would complete an additional CGI-P (see "Baseline Re-Assess," above).

† Post-treatment assessment also functions as the baseline assessment for those in waitlist condition, who cross over into compassionate care. † indicates supplemental measures added only for compassionate care baseline.

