feel that life is empty or wonder if it's worth living"; 2: I think of suicide or death several times a week for several minutes"; and 3: "I think of suicide or death several times a day in some detail, or I have made specific plans for suicide or have actually tried to take my life". Scores on the QIDS-SR were used to evaluate eligibility at the screening visit, and to measure self-reported depressive symptoms at subsequent assessment visits. The QIDS-SR i12 was delivered weekly to participants via the app (in the active group) or via REDCap (in the waitlist group) to monitor for risk concerns during the trial. Scores >0 triggered a popup message to the participant about calling 911/going to the ER, and participants were provided information about contacting a suicide hotline. Scores >1 also triggered a text message alert to the coach with the specific item response given by the participant (i.e., 2 vs. 3). Study clinicians followed up with the participant within 24 hours by phone to assess for risk, and to refer to a higher level of care if clinically indicated (see Minimizing Risks, below). After an initial alert for a participant, study clinicians used clinical judgement when determining follow-up for additional alerts.

Columbia-Suicide Severity Rating Scale (C-SSRS): The C-SSRS (Posner et al., 2011) is a gold-standard, clinician-administered assessment of suicidal ideation and suicide behaviors. The baseline version, which assesses both lifetime and recent time frames, was used to establish eligibility at the baseline/screening visit. The "Update" version, which assesses suicide risk since the last assessment, was used at subsequent study administrations.

Body Parts of Concern List: This list names a wide range of body parts that are the most common areas of appearance concerns for BDD patients. The measure asks participants to indicate which body parts they are preoccupied with.

Assessment of Functioning and Quality of Life

Sheehan Disability Scale (SDS): The SDS uses a Likert scale from 0 (not at all) to 10 (extremely) to assess impairment in occupational, social, and family domains. It has strong internal consistency and validity (Sheehan et al., 1996).

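### Read as a difference in week-12 level, the primary test makes almost no use of baseline BDD-YBOCS; giving both arms one baseline mean would add precision with no new data.

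*Combined protocol and SAP*

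**What the plan says.** Section VI.B gives the primary endpoint as "Difference in BDD severity (BDD-YBOCS) at the end of treatment/waitlist period". The model in VI.C "included time (categorical; baseline, mid-point, and end-of-treatment), treatment (app-CBT vs. waitlist), and their interaction as fixed effects", with the covariance structure chosen among four candidates by AIC and BIC. The test is described in one sentence: "The main hypothesis test was based on a specific contrast of treatment difference at week 12". No contrast coefficients are given, and no baseline covariate or equal-baseline constraint appears anywhere in section VI. Hypothesis 1 speaks of greater improvement, which is the language of change, whereas the endpoint speaks of a difference in severity.

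For the secondary outcomes, VI.C says: "We used the same hierarchical mixed model approach as described for the primary endpoint".

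Three statements elsewhere bear on the remedy:

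- Sections IV.A and IV.B place the evaluator's baseline interview before randomization of eligible participants. Section V, however, says of the self-report measures: "Following screening and randomization, participants completed self-report measures for the baseline assessment through a secure REDCap link emailed to them".
- The note to Table 1 covers cases where more than ten days pass between the "initial baseline screening assessment and the start of treatment, the study IE would re-administer the AE form, AE log, BDD-YBOCS, BABS" and other forms. It does not say whether this repeat comes before randomization.
- The measure descriptions add: "Scores on the QIDS-SR were used to evaluate eligibility at the screening visit".

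**The concern.** A model with a separate mean for every arm and visit ties nothing at week 12 to baseline. Baseline BDD-YBOCS can then influence the week-12 contrast only through participants whose week-12 score is missing. Yet the arms come from one randomized population, so their expected baseline means are equal. The planned model does not use that fact.

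Two consequences follow. The confidence interval for the primary effect is wider than the collected data require. A chance difference in baseline severity also carries through to the estimate. Randomization was stratified only by medication status (IV.B). Section VI compares the arms at baseline but states no consequence for the model if they differ.

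**Working it through.** **1. The plan's own figure.** Inputs from VI.D: two-sided alpha 0.05, power 0.90, equal allocation, 15% drop-out, d = 0.90 and then 0.81. A two-sample t calculation gives:

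- d = 0.90: 27 evaluable per arm (power 0.901); 27/0.85 = 31.8, so 32 per arm and 64 in total.
- d = 0.81: 34 evaluable per arm (power 0.908); 34/0.85 = 40 per arm and 80 in total.

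Both match the document. The trial was sized as an unadjusted week-12 comparison, which supports reading the contrast as a difference in level.

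**2. Complete data.** Take SD = 1, n = 40 per arm, and ρ for the baseline-to-week-12 correlation. The documents do not give ρ, so 0.3 to 0.6 is assumed.

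- Planned level contrast: variance 2/n = 0.0500 at every ρ.
- Common baseline mean: the estimate is the week-12 difference minus ρ times the baseline difference, with variance (2/n)(1 − ρ²) = 0.0455, 0.0420, 0.0375 and 0.0320 at ρ = 0.3, 0.4, 0.5 and 0.6.

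**3. With 15% drop-out.** The variance is the relevant element of (Σ X′V⁻¹X)⁻¹ over participants. Further assumptions: half of those missing week 12 also miss week 6, corr(week 6, week 12) = 0.7, corr(baseline, week 6) = ρ + 0.1, and the same SDs and correlations in both arms. Power is Φ(d/SE − 1.96).

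| ρ | SE, planned level | SE, common baseline | Variance ratio | Equivalent n per arm (40/ratio) | Power at d = 0.81 | Power at d = 0.60 |
|---|---|---|---|---|---|---|
| 0.3 | 0.237 | 0.227 | 0.920 | 43 | 0.928 → 0.946 | 0.717 → 0.752 |
| 0.4 | 0.236 | 0.219 | 0.857 | 47 | 0.929 → 0.959 | 0.719 → 0.783 |
| 0.5 | 0.235 | 0.207 | 0.774 | 52 | 0.931 → 0.974 | 0.722 → 0.825 |
| 0.6 | 0.234 | 0.192 | 0.672 | 60 | 0.933 → 0.988 | 0.726 → 0.878 |

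Example at ρ = 0.5: 0.81/0.2354 − 1.96 = 1.48, giving 0.931; 0.81/0.2072 − 1.96 = 1.95, giving 0.974. The planned power here is a little above 0.908 because it uses the normal approximation and because the mixed model recovers some information from drop-outs' earlier visits. Under compound symmetry at the same ρ, the variance ratios are nearly identical: 0.922, 0.860, 0.778 and 0.674.

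**4. If the contrast is a difference in change.** Its SEs are 0.276, 0.257, 0.235 and 0.212. The ratios of constrained variance to these are 0.678, 0.726, 0.775 and 0.822, so the constraint cuts the variance by 32%, 27%, 23% or 18%.

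**5. Chance imbalance.** The baseline difference has SE √(2/40) = 0.224 SD. The chance that it exceeds 0.2 SD in either direction is P(|Z| > 0.2/0.224) = 0.37. Such a gap moves the planned estimate by ρ × 0.2 = 0.06 to 0.12 SD, or 7% to 15% of 0.81. This is sampling error, not bias.

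**6. Validity of adjusting.** A simulation of 3,000 runs (34 per arm, complete data, baseline-adjusted ANCOVA standing in for the constrained model) gave type I error of 0.046 to 0.052 across ρ = 0.3, 0.5 and 0.7. At ρ = 0.5, power was 0.961, against 0.911 for the raw week-12 difference.

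**The case against.** The strongest reply is that nothing is broken. The planned test has the right type I error, matches the stated endpoint and agrees with the sample-size calculation. That stands: this is a choice of a more efficient estimator, not the repair of an error.

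Second, much of section VI is in the past tense and reads as a report of analyses already run, so the power gains may no longer be available by redesign. This limits the remedy to a sensitivity analysis if it is so. It does not remove the point.

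Third, if a difference in change was meant, baseline is used and its imbalance is subtracted. At ρ = 0.6 that contrast has about 18% less variance than the level contrast (0.212² against 0.234²). The statement about almost no precision gain therefore applies to the level reading only. The constrained model is still the more precise under either reading.

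Fourth, precision and protection against imbalance are one gain, not two: with complete data the variance saved, 0.05ρ², is exactly the variance of the imbalance-driven shift. This is correct. A shift of 0.06 to 0.12 SD is a quarter to a half of one SE (0.235) and already lies within the planned interval's uncertainty.

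Fifth, the size rests on an assumed ρ and on equal covariances in a treated and a waiting arm. At ρ = 0.3 the gain is small. An older baseline, used where a re-assessment exists, might correlate less with week 12 and shrink it further. These limits stand.

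**Conclusion.** The concern holds as a recommended improvement. On the level reading, which the endpoint wording and the reproduced sample sizes favour, the planned contrast gains almost nothing from baseline BDD-YBOCS. A common baseline mean would reduce its variance by 8%, 14%, 23% or 33% at assumed correlations of 0.3, 0.4, 0.5 or 0.6. The trial does not need this to reach its stated power; the benefit is a narrower interval and more power should the effect be smaller than 0.81. The direction does not depend on which contrast was intended, but the size does depend on a correlation that the documents do not supply.

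**What to change.** For BDD-YBOCS, keep the three visits and the intent-to-treat set, but fit one baseline mean for both arms, with treatment effects at weeks 6 and 12 only, and test the week-12 effect. In addition:

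- Write out the contrast coefficients.
- Use the initial pre-randomization evaluator rating as baseline for everyone, and state how any re-assessment value is handled.
- Apply the same constraint to BABS. Apply it to QIDS-SR only if the value analysed is the pre-randomization screening score.
- Keep the planned model for SDS and Q-LES-Q. Their baselines were completed after randomization, so equal means are not guaranteed.
- Do not move baseline to a covariate, because that would drop participants with only a baseline, whom section VI counts in the intent-to-treat sample. The reason is who is counted, not precision: in the constrained model these participants leave the week-12 SE unchanged to four decimals.

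If outcomes have not been analysed, the cost is a short SAP edit and one model statement, with no new data. The secondary outcomes would then no longer all share one model form, which the SAP should say. If outcomes have been analysed, the planned primary result stays as it is and the constrained model is reported as a labelled sensitivity analysis.
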